3.1.1 Pharmaceutical and Therapeutic Background

The importance of intact immune surveillance in controlling outgrowth of neoplastic transformation has been known for decades. The PD-1 receptor-ligand interaction is a major pathway utilized by tumors to suppress the anti-tumor immune response. PD-1 is expressed on the cell surface of activated T-cells under healthy conditions, and it serves to down-modulate unwanted to excessive immune responses, such as autoimmune reactions. PD-1 (encoded by the gene Pdcd1) is an Ig superfamily member related to CD28 and CTLA-4 which has been shown to negatively regulate antigen receptor signaling upon engagement of its ligands (PD-L1 and/or PD-L2). PD-1 and family members are type I transmembrane glycoproteins containing an Ig Variable-type (V-type) domain responsible for ligand binding and a cytoplasmic tail which is responsible for the binding of signaling molecules. The cytoplasmic tail of PD-1 contains 2 tyrosine-based signaling motifs, an immunoreceptor tyrosine-based inhibition motif (ITIM) and an immunoreceptor tyrosine-based switch motif (ITSM). Following T-cell stimulation, PD-1 recruits the tyrosine phosphatases SHP-1 and SHP-2 to the ITSM motif within its cytoplasmic tail, leading to the dephosphorylation of effector molecules such as CD3ζ, PKCθ and ZAP70 which are involved in the CD3 T-cell signaling cascade. The mechanism by which PD-1 down modulates T-cell responses is similar to, yet distinct from that of CTLA-4 as both molecules regulate an overlapping set of signaling proteins. PD-1 was shown to be expressed on activated lymphocytes including peripheral CD4+ and CD8+ Tcells, B-cells, T regs and Natural Killer cells. Expression has also been shown during thymic development on CD4-CD8- (double negative) T-cells as well as subsets of macrophages and dendritic cells. The ligands for PD-1 (PD-L1 and PD-L2) are constitutively expressed or can be induced in a variety of cell types, including non-hematopoietic tissues as well as in various tumors. Both ligands are type I transmembrane receptors containing both IgV- and IgC-like domains in the extracellular region and contain short cytoplasmic regions with no known signaling motifs. Binding of either PD-1 ligand to PD-1 inhibits T-cell activation triggered through the T-cell receptor. PD-L1 is expressed at low levels on various non-hematopoietic tissues, most notably on vascular endothelium, whereas PD-L2 protein is only detectably expressed on antigen-presenting cells found in lymphoid tissue or chronic inflammatory environments. PD-L2 is thought to control immune T-cell activation in lymphoid organs. whereas PD-L1 serves to dampen unwarranted T-cell function in peripheral tissues. Although healthy organs express little (if any) PD-L1, a variety of cancers were demonstrated to express abundant levels of this T-cell inhibitor. PD-1 has been suggested to regulate tumor-specific Tcell expansion in subjects with melanoma. This suggests that the PD-1/PD-L1 pathway plays a critical role in tumor immune evasion and should be considered as an attractive target for therapeutic intervention.

Nivolumab is a human IgG4 monoclonal antibody that binds to the PD-1 receptor and blocks the interaction between PD-1 and its ligands, PD-L1 and PD-L2. Nivolumab is approved in the United Stated for the treatment of patients with unresectable or metastatic melanoma. It is

also indicated in the setting of disease progression following ipilimumab and/or a BRAF inhibitor (if BRAF V600E mutation positive).

VEGF, produced by endothelial cells, is critical for the regulation of both physiologic and pathologic angiogenesis.¹⁷ This process plays a key role in tumor growth and metastasis. VEGF (also known as VEGF-A) is one of the members of the VEGF family also comprised of VEGF-B, VEGF-C, VEGF-D, and placenta growth factor (PLGF). Each member is uniquely expressed with varying receptor specificity and function. 18 VEGF is encoded by a transcript composed of 8 exons and 7 introns. Through alternative splicing, several different isoforms are generated with each isoform having differing degrees of pro-angiogenic properties.¹⁹ VEGF expression is further regulated by the tumor environment, predominantly by hypoxia, which induces the transcription factor HIF1a, leading to increased VEGF expression.²⁰ The members of the VEGF family bind to varying combinations of VEGF receptors; VEGF binds only to VEGFR-1 and VEGFR-2, while VEGFR-3 binds VEGF-C and VEGF-D. VEGFR-1 through 3 are tyrosine kinase receptors with similar structures consisting of an extracellular domain of 7 IgG folds, a single transmembrane domain, and split tyrosine kinase domain. Binding of the ligand to the receptor induces dimerization of the receptor which is necessary for downstream signaling. Of note, the VEGFR-2 has been identified as the major mediator of VEGF induced angiogenesis, VEGFR-3 is involved in angiolymphogenesis, and the exact role of VEGFR-1 is not fully understood.

Axitinib is a second-generation tyrosine kinase inhibitor of VEGFR-1, VEGFR-2, and VEGFR-3. Axitinib is approved by the FDA for the treatment of metastatic renal cell carcinoma alone and more recently in conjunction with either pembrolizumab or avelumab in the first line setting. ^{21,22}

3.1.2 Preclinical and Clinical Trial Data

Nivolumab: Refer to the Investigator's Brochure for Preclinical and Clinical data of Nivolumab.

Axitinib: Refer to the Investigator's Brochure for Preclinical and Clinical data of Axitinib.

3.2 Rationale

3.2.1 Rationale for the Trial and Selected Subject Population

The critical role of angiogenesis in cancer biology has long been appreciated, and antiangiogenic therapies have been successfully utilized in several cancer types, including renal cell carcinoma and colorectal cancer. However, while the significance of anti-angiogenic therapy was first thought to be related to decreasing tumor blood supply, it is now appreciated that its effect on oxygen tension and immune infiltration are critical in maintaining antitumor activity, and that normalization of the blood supply may help the immune response. Melanoma is understood to be an angiogenic tumor, with new vessel formation implicated in the progression from atypical melanocyte, to horizontal growth phase, and subsequently to the more aggressive vertical growth phase.^{23,24} Increased VEGF expression is associated with a greater depth of invasion. ²⁵ Bevacizumab is an anti-VEGF monoclonal antibody that has been evaluated as monotherapy in the adjuvant setting, as well as in combination with chemotherapy or anti-CTLA4 in the advanced setting, with mostly disappointing results. ²⁶⁻³⁰ Axitinib, on the other hand, is a small molecule inhibitor of the VEGF receptor and binds to VEGFR-1, VEGFR-2, and VEGFR-3. Axitinib monotherapy has been evaluated in patients with advanced melanoma, with an ORR of 18.8% in the first line setting.³¹ A phase II trial of axitinib with carboplatin and paclitaxel yielded an ORR of 22% and median PFS of 8.7 months.³² A more recent phase IB trial evaluated toripalimab (anti-PD1) and axitinib in 33 patients with treatment naive metastatic melanoma. No dose limiting toxicities were observed, and by the cut-off date, 14/29 (48.3%) patients achieved an objective response, which is higher than would be expected with anti-PD1 monotherapy. 16 However, it must be noted that 88% of these patients had mucosal melanoma. Our preclinical data suggests that although high dose axitinib exacerbates hypoxia, low dose axitinib improves hypoxia. We hypothesize this is through normalization of aberrant tumor vasculature, which allows for improved tumor perfusion and immune cell infiltration. We have previously shown that T cells in a hypoxic TME are exhausted and dysfunctional. 10,33-35 Thus, combining axitinib with anti-PD1 may salvage a portion of patients with anti-PD1 refractory disease, which is supportive of other previously published findings utilizing immunotherapy with VEGF targeting. 36-38 We therefore propose a phase II investigator-initiated study of nivolumab plus axitinib in patients with unresectable stage III or IV melanoma who have progressed on anti-PD1 therapy.

3.2.2 Rationale for Dose Selection/Regimen/Modification

The choice for 480 mg every 4 weeks of nivolumab was made based on standard clinical practice in patients with melanoma. Initial pharmacokinetics assessed using the population PK model of nivolumab found that nivolumab had a wide therapeutic index from 0.1 to 10 mg/kg every 2 weeks. The 3 mg/kg dose was found to be effective in phase III studies across tumor types and was approved by the FDA. Subsequently, a fixed dose of 240 mg every 2 weeks was approved based on comparable safety and efficacy data. A fixed dose simplifies the dosing regimen, which is both more convenient for physicians and reduces potential for dosing errors. More recently, the FDA has expanded the approval to include 480 mg every 4 weeks based on safety and efficacy data that suggested this dosing was comparable to 3 mg/kg every 2 weeks. This dosing regimen provides additional convenience for patients, particularly those who will be treated over a long timeframe, such as our cohort.

Regarding axitinib, 5 mg twice daily is the standard FDA approved dose. In a murine B16 melanoma model, we administered vehicle, axitinib at a low dose (10 mg/kg), or axitinib at a high dose (50 mg/kg) for 4 days. We found that high dose axitinib exacerbates hypoxia, while low dose axitinib lowers intra-tumoral hypoxia (**Figure 6**). Importantly, the standard dose of axitinib (5 mg BID) corresponds to the low dose used in our murine models.

3.2.3 Rationale for Endpoints

3.2.3.1 Efficacy Endpoints

The primary endpoint is the overall response rate after treatment with nivolumab plus axitinib. We hypothesize that patients treated with nivolumab plus axitinib will have a greater response rate compared to historical responses in anti-PD1 refractory patients, which is estimated to be 10%, based on responses to ipilimumab after anti-PD1 therapy. An ORR of 25% or higher would be of clinical interest. We hypothesize that the mechanism by which there will be an improved response rate is that the addition of low dose axitinib will renormalize tumoral vasculature, improve tumor perfusion, immune infiltration, and reduce hypoxia. Our preclinical model was notable for a reduction in hypoxia seen in the low-dose group. Secondary efficacy endpoints include safety, PFS, and OS. The combination of pembrolizumab plus axitinib has been approved by the FDA for advanced renal cell carcinoma, and its toxicity profile is well-established. Here, we will use nivolumab in place of pembrolizumab. Nivolumab and pembrolizumab are virtually identical in terms of cellular target and known toxicity, thus we expect toxicity rate of the current combination therapy and dose to be acceptable. We hypothesize that treatment with nivolumab plus axitinib will prolong both PFS and OS.

3.2.3.2 Biomarker Research

The secondary endpoints of this study seek to identify the functional consequences of axitinib-induced remodeling of the tumor microenvironment with concomitant anti-PD1 blockade. We will analyze biopsy samples prior to treatment with axitinib plus nivolumab as well as 12 weeks after treatment. First, we will immunophenotype the TIL from patient tumor samples using antibodies to T cell markers (CD4, CD8, PD1, TIM-3, CD45RO, CD45RA, FOXP3, among others) via 14-color flow cytometry. Second, we will profile intra-tumoral hypoxia and immune architecture of patient samples, assessed via staining for CAIX, HIF1a, and VEGF utilizing highly multiplexed immunofluorescent imaging (CODEX) and pimonidazole CITE-seq to evaluate transcriptional changes. Third, we will assess proliferation and functional analysis with Ki-67 and cytokine production of TIL. Lastly, we will also metabolically profile the biopsies utilizing Seahorse.

4.0 METHODOLOGY

4.1.1 Subject Inclusion Criteria

In order to be eligible for participation in this trial, the subject must:

- 1. Be willing and able to provide written informed consent for the trial.
- 2. Be \geq 18 years of age on day of signing informed consent.

- 3. Have unresectable (stage III) or advanced (stage IV) cutaneous or mucosal melanoma. Patients with uveal melanoma are not eligible.
- 4. Progressed on prior anti-PD1 therapy with or without anti-CTLA4 therapy. Patients may have progressed in the adjuvant setting if treated within the last 6 months. Prior treatment with BRAF/MEK inhibitors permitted, however, not required. Progression must be radiographic, and progression of disease will be confirmed by a radiologist. Patients must have progressed during anti-PD-1 therapy, defined as unequivocal progression on or within 3 months of the last dose of anti-PD-1 therapy if treated in the metastatic setting, or within 6 months if treated in the adjuvant setting.
- 5. Have measurable disease based on RECIST 1.1.
- 6. Patients do not have to have biopsiable disease to be eligible. However, patients with biopsiable disease must undergo biopsy at study entry and at week 12.
- 7. Have a performance status of 0 or 1 on the ECOG Performance Scale.
- 8. Demonstrate adequate organ function as defined in Table 1. All screening labs should be performed within 14 days of treatment initiation.

Table 1: Adequate Organ Function Laboratory Values

Criston	Laboratory Volus			
System	Laboratory Value			
Hematological				
Absolute neutrophil count (ANC)	≥1,000 /mcL			
Platelets	≥50,000 / mcL			
TT 11.	≥7 g/dL without transfusion or EPO dependency (within 7 days			
Hemoglobin	of assessment)			
Renal				
Serum creatinine OR	≤1.5 X upper limit of normal (ULN) OR			
Measured or calculated creatinine	\ \ \ \ \ \ \ \ \ \ \ \ \ \ \ \ \ \ \			
clearance	\geq 60 mL/min for subject with creatinine levels \geq 1.5 X			
(GFR can also be used in place of	institutional ULN			
creatinine or CrCl*)				
Hepatic				
Serum total bilirubin	≤ 1.5 X ULN OR			
	Direct bilirubin ≤ ULN for subjects with total bilirubin levels >			
	1.5 ULN			
ACT (CCOT) = 1 ALT (CCDT)	≤ 2.5 X ULN OR			
AST (SGOT) and ALT (SGPT)	≤ 5 X ULN for subjects with liver metastases			
Coagulation				
International Normalized Datic (IND) or	≤1.5 X ULN unless subject is receiving anticoagulant therapy			
International Normalized Ratio (INR) or	as long as PT or PTT is within therapeutic range of intended use			
Prothrombin Time (PT)	of anticoagulants			
Astivated Partial Thrombonlastin Time	≤1.5 X ULN unless subject is receiving anticoagulant therapy			
Activated Partial Thromboplastin Time	as long as PT or PTT is within therapeutic range of intended use			
(aPTT)	of anticoagulants			
*Creatinine clearance should be calculated per institutional standard.				

- 9. Patients with brain metastases are permitted if they are asymptomatic or previously treated with CNS directed therapy with stable CNS disease for at least 2 weeks. Stable is defined as asymptomatic or not progressing on imaging.
- 10. Female patients of childbearing potential must have a negative urine or serum pregnancy test within 7 days from the time of registration. Also, within 24 hours prior to receiving the first dose of study medication then every 4 weeks while on treatment.
- 11. Female subjects of childbearing potential should be willing to use 2 methods of birth control or be surgically sterile or abstain from heterosexual activity for the course of the study and for 5 months after the last dose of study medication. Subjects of childbearing potential are those who have not been surgically sterilized or have not been free from menses for > 1 year.
- 12. Male subjects should agree to use an adequate method of contraception starting with the first dose of study therapy through 7 months after the last dose of study therapy.

Note: Abstinence is acceptable if this is the usual lifestyle and preferred contraception for the subject.

4.1.2 Subject Exclusion Criteria

The subject will be excluded from the trial if the subject:

- 1. Prior history of Grade 3 or 4 immune-related adverse events or immune-related adverse events requiring discontinuation of prior therapies.
- 2. History of hypertensive crisis or hypertensive encephalopathy
- 3. Significant thrombotic (e.g, deep vein thrombosis or pulmonary embolism) or hemorrhagic event within 6 months prior to enrollment).
- 4. Has a history of prior immune-related adverse event due to an anti-PD1 or anti-CTLA4 that has not resolved to grade 1 on a steroid dose of prednisone 10 mg or less at the time of study entry (excluding vitiligo and endocrine toxicity).
 - Patients with prior myocarditis or other immune-mediated cardiac adverse events are excluded regardless of grade.
 - Patients with prior Guillain-Barre syndrome, encephalitis, meningitis, or transverse myelitis are excluded regardless of grade.

- Patients with prior Stevens-Johnson syndrome or toxic epidermal necrolysis are excluded regardless of grade.
- 5. Has poorly controlled hypertension defined as systolic blood pressure (SBP) > 160 and/or diastolic blood pressure (DBP) > 100 despite antihypertensives. If subject is above this goal, treatment with anti-hypertensives to achieve better blood pressure control is permitted. Ambulatory blood pressure assessment is permitted if there is concern for discrepant blood pressure readings while patients are in clinic. Note: measurement of screening blood pressure (BP) reading is based on an average of 3 readings at least 2 minutes apart if the subject has an initial BP ≥150/90. Subjects with initial screening BP ≥150/90 mmHg can be treated with anti-hypertensive medication to achieve a well-controlled status and are eligible with reassessed SBP/DBP of < 160/100 mm Hg.
- 6. Has Class III or IV heart failure based on the New York Heart Association
- 7. Has had major surgery within 4 weeks of randomization. This does not include outpatient surgeries that do not require post-operative admission.
- 8. Has a diagnosis of immunodeficiency or is receiving systemic steroid therapy (greater than the equivalent of prednisone 10 mg daily, unless for prior endocrine toxicity) or any other form of immunosuppressive therapy within 7 days prior to the first dose of trial treatment. Premedication with steroids for contrast imaging studies is permitted.
- 9. Has a known history of active TB (Bacillus Tuberculosis).
- 10. Hypersensitivity to nivolumab or axitinib, or any of their excipients.
- 11. Has had prior chemotherapy or targeted small molecule therapy within 1 week prior to study Day 1 or who has not recovered (i.e., ≤ Grade 1 or at baseline) from adverse events due to a previously administered agent.
 - Note: Subjects with ≤ Grade 2 neuropathy are an exception to this criterion and may qualify for the study.
 - Note: If subject received major surgery, they must have recovered adequately from the toxicity and/or complications from the intervention prior to starting therapy.
- 12. Has had radiation within 2 weeks of randomization
- 13. Has current use or anticipated need for treatment with drugs or foods that are known strong cytochrome P450 (CYP34A4/5) inhibitors including but not limited to atazanavir, clarithromycin, indinavir, itraconazole, ketoconazole, nefazodone,

nelfinavir, ritonavir, saquinavir, telithromycin, troleandomycin, voriconazole, and grapefruit or grapefruit juice. NOTE: The topical use of these medications, such as 2% ketoconazole cream is allowed.

- 14. Has current use or anticipated need for treatment with drugs known to be strong CYP3A4/5 inducers, including but not limited to carbamazepine, phenobarbital, phenytoin, rifabutin, rifampin, and St. John's wort.
- 15. Has a known additional malignancy that is progressing or requires active treatment. Exceptions include basal cell carcinoma of the skin or squamous cell carcinoma of the skin that has undergone potentially curative therapy, in situ cervical cancer, in situ colon cancer, or nonmetastatic prostate cancer not on systemic therapy.
- 16. Has known active central nervous system (CNS) metastases and/or carcinomatous meningitis. Subjects with previously treated brain metastases may participate provided they are stable (without evidence of progression by imaging for at least 2 weeks prior to the first dose of trial treatment and any neurologic symptoms have returned to baseline), have no evidence of new or enlarging brain metastases, and are not using steroids for at least 7 days prior to trial treatment. This exception does not include carcinomatous meningitis which is excluded regardless of clinical stability.
- 17. Has active autoimmune disease that has required systemic treatment in the past 2 years (i.e. with use of disease modifying agents, corticosteroids or immunosuppressive drugs). Replacement therapy (e.g., thyroxine or physiologic corticosteroid replacement therapy for adrenal or pituitary insufficiency, etc.) is not considered a form of systemic treatment
- 18. Has a history of (non-infectious) pneumonitis that required steroids or current pneumonitis.
- 19. Has an active infection requiring systemic IV antibiotic therapy.
- 20. Has had any of the following within the past 6 months
 - Myocardial infarction or unstable angina
 - Ventricular arrythmia
 - Acute decompensated heart failure
 - Cerebrovascular accident
 - Hypertensive emergency requiring ICU admission

- 21. Presence of a disorder that may impact absorption of axitinib, such as inability to take oral medication, requirement for IV alimentation, prior gastric resection, treatment for active peptic ulcer confirmed by endoscopy within the past 3 months, active GI bleed, malabsorption syndrome.
- 22. Has a history or current evidence of any condition, therapy, or laboratory abnormality that might confound the results of the trial, interfere with the subject's participation for the full duration of the trial, or is not in the best interest of the subject to participate, in the opinion of the treating investigator.
- 23. Has known psychiatric or substance abuse disorders that would interfere with cooperation with the requirements of the trial.
- 24. Is pregnant or breastfeeding or expecting to conceive or father children within the projected duration of the trial, starting with the pre-screening or screening visit through 5 months after the last dose of trial treatment for females and 7 months after the last dose of trial treatment for males.
- 25. Has a known history of Human Immunodeficiency Virus (HIV) (HIV 1/2 antibodies) if the CD4 count is less than 350 mm3 or serum HIV viral load is < 25,000 IU/mL.
- 26. Has a known history of or is positive for hepatitis B (hepatitis B surface antigen [HBsAg] reactive) or hepatitis C (hepatitis C virus [HCV] RNA [qualitative] is detected). Note: Without known history, testing only needs to be performed if there is clinical suspicion for Hepatitis B or C.
- 27. Is currently incarcerated or otherwise detained.
- 28. Has received a live vaccine within 30 days of planned start of study therapy.

Note: Seasonal influenza vaccines for injection are generally inactivated flu vaccines and are allowed; however intranasal iNinfluenza vaccines (e.g., Flu-Mist®) are live attenuated vaccines, and are not allowed.

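### Exclusion criterion 25 has its HIV viral-load inequality reversed relative to its CD4 limb: it excludes well-controlled infection and lets high viral load through

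*Combined protocol and SAP*

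**What the plan says.** Section 4.1.2 is an exclusion list. Its lead-in reads "The subject will be excluded from the trial if the subject", so a condition that is true removes the patient. Criterion 25 opens with "Has a known history of Human Immunodeficiency Virus (HIV) (HIV 1/2 antibodies" and then narrows the exclusion to two situations joined by a plain *or*: "if the CD4 count is less than 350 mm3 or serum HIV viral load is < 25,000 IU/mL".

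No other part of the document sets an HIV viral-load rule. Two other exclusion criteria might touch the same patients without naming HIV, CD4 or viral load: criterion 8, "Has a diagnosis of immunodeficiency or is receiving systemic steroid therapy", and criterion 22, "Has a history or current evidence of any condition, therapy, or laboratory abnormality that might confound the results of the trial", which is left to the treating investigator's opinion.

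**The concern.** A low CD4 count and a high viral load both indicate poorly controlled HIV. A criterion that admits some patients with HIV and excludes others would be expected to exclude on low CD4 and on high viral load. Criterion 25 excludes on low CD4 and on *low* viral load, so the two limbs cannot serve one purpose.

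Two things are at stake:

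- **Who is treated.** Followed exactly, the rule refuses the patients with HIV who are most suitable for a checkpoint-inhibitor trial and presents no barrier, at this criterion, to those with substantial viraemia and CD4 of 350 or more.
- **How site staff can act.** Section 5.1.1.2 requires every criterion to be reviewed. Section 8.4 allows a departure from the approved protocol without prior IRB approval only to remove an immediate hazard. A site that enrols a well-controlled patient on the presumed intent commits a protocol deviation. Section 6.4.1 limits the DLT-evaluable, response-evaluable and safety sets to study-eligible patients, so that patient could also be dropped from those sets after receiving drug.

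**Working it through.** The plan has no figure to reproduce here. The check is of the criterion's logic.

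**Inputs, all from Section 4.1.2**

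- Direction of the list: a true condition excludes.
- Scope of criterion 25: known HIV.
- Limb A: CD4 < 350 (read as cells per mm³).
- Limb B: viral load (VL) < 25,000 IU/mL.
- Connector: *or*.

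**Rule as written:** exclude if (CD4 < 350) or (VL < 25,000).

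Negating it gives the patients who pass criterion 25: CD4 ≥ 350 *and* VL ≥ 25,000.

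**Comparison rule, viral-load sign reversed:** exclude if (CD4 < 350) or (VL > 25,000).

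**Alternative reading, *or* taken as *and*:** exclude if (CD4 < 350) and (VL < 25,000).

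The rules were evaluated at CD4 200, 349, 350 and 600. Results were the same for 200 and 349, and the same for 350 and 600, so the rows are merged.

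| CD4 | VL (IU/mL) | As written | Sign reversed | *And* reading |
|---|---|---|---|---|
| 200 or 349 | 0; 50; 24,999 | excluded | excluded | excluded |
| 200 or 349 | 25,000; 100,000; 1,000,000 | excluded | excluded | passes |
| 350 or 600 | 0; 50; 24,999 | **excluded** | passes | passes |
| 350 or 600 | 25,000 | passes | passes | passes |
| 350 or 600 | 100,000; 1,000,000 | **passes** | excluded | passes |

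**What the table shows**

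1. Below CD4 350, limb A decides and the sign in limb B makes no difference.
2. At CD4 350 or above, limb B alone decides. There the written rule gives the opposite answer to the sign-reversed rule at every viral load tested except exactly 25,000, where both let the patient pass.
3. Reading *or* as *and* does not rescue the text. It would exclude only patients with both low CD4 and low viral load, and would let through those with low CD4 and high viral load, the worst-controlled group.

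**Direction of neighbouring criteria.** Criterion 26 excludes when hepatitis C RNA is found, so there viraemia excludes. Criterion 5 excludes poorly controlled blood pressure and accepts the patient once it is controlled. The viral-load limb of criterion 25 runs the other way.

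**The case against.** The strongest case against giving this weight has five parts.

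- **Passing criterion 25 is not the same as being eligible.** A viraemic patient must still clear criterion 8 (immunodeficiency), criterion 13 (strong CYP3A4/5 inhibitors, a list that includes atazanavir, indinavir, nelfinavir, ritonavir and saquinavir) and criterion 22 (investigator's opinion). This stands as a limit on the safety risk: an investigator can refuse such a patient. But none of these criteria sets a viral-load rule, and none can restore eligibility to a well-controlled patient whom criterion 25 excludes.
- **The analysis-set consequence is limited.** Section 6.4.1 bases the intent-to-treat analyses of response and survival on everyone treated, with no eligibility condition, and a patient enrolled under the literal criterion is eligible by that same text. This stands. Set membership is at risk only for a patient enrolled against the literal wording, and only in the three sets restricted to eligible patients.
- **Few patients are affected.** The trial enrols 31, the criterion concerns known HIV only, and neither the flow chart in Section 5.1 nor Table 7 lists an HIV, CD4 or viral-load test. The number affected could be zero. This also stands.
- **It is a drafting slip rather than a choice of design.** Probably so, but the slip sits in an operative threshold, not in background text.
- **The symbol may have been misread when the PDF was converted.** This cannot be excluded from text alone, and some symbols in Table 1 of Section 4.1.1 are damaged. The inequalities in criterion 5 of the same exclusion list are intact and sensible, however, and nothing points to a misreading in criterion 25.

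**Conclusion.** Criterion 25 is wrong as written. Among patients with known HIV and CD4 of at least 350, it excludes every viral load below 25,000 and passes every viral load of 25,000 or more. Patients with high viral load pass only if CD4 is also at least 350, because the CD4 limb still removes the rest.

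The consequence is for eligibility and patient protection. No estimate, test or decision boundary moves, and the sample size, type I error and power of the two-stage design are unaffected. The documents do not say how many patients with HIV are expected; among 31 it is probably very few and may be none.

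The conclusion rests on two assumptions: that the extracted symbol matches the page, and that the CD4 limb shows the intended direction. The documents do not state the intended viral-load rule, so the direction is inferred and the sponsor must confirm it.

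**What to change.** Restate criterion 25 so that both limbs exclude poorer control: known HIV with CD4 below 350 cells/mm³, or viral load above 25,000 IU/mL. The sponsor should confirm three things: the direction, that 25,000 is the intended clinical threshold, and whether a value of exactly 25,000 excludes.

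With the sign reversed, patients with CD4 of at least 350 and viral load below 25,000 pass the criterion, those above 25,000 are excluded, and everyone with CD4 below 350 remains excluded.

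The cost is one symbol in the next protocol amendment, with no change to the statistical design. Until it is approved, sites should refer any candidate with known HIV to the sponsor before enrolment, and any patient with HIV already screened should be checked against the corrected rule.
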